Superior Hypogastric Blockade for Postoperative Pain

[name] [name]^{1,2}, [name], Prof³, [name], MD³, [name],
Assoc. Prof¹

1: University of Health Sciences, Kocaeli Derince Training and Research Hospital, Department of Anesthesiology and Reanimation, [name].

2: Kocaeli University School of Medicine, Department of Anatomy (PhD student), Kocaeli, Turkey.

3: University of Health Sciences, Kocaeli Derince Training and Research Hospital, Department of Gynecology and Obstetrics, [name].

Trial registration: NCT03428152

Date of the document:

Initial Release: January 30th, 2018

Study Start (Actual): February 9th, 2018

Study Completion (Actual): July 24th, 2018

Last Update: February 17th, 2019

Objectives: Total abdominal hysterectomy cause significant postoperative pain. Intraoperative superior hypogastric block may be an alternative way for acute postoperative pain relief in patients undergoing hysterectomy. This study's objective is to evaluate the effect of intraoperative superior hypogastric blocks on postoperative pain management.

Design and Subjects: Sixty female patients who underwent elective abdominal hysterectomy were included in the prospective observational cohort study. Patients were divided into two groups: Patients who had intraoperative SHP block (Hypo; n=30), and patients who did not have intraoperative SHP block (No-Hypo; n=30).

Methods: Total sample size was determined by performing a power analysis. Thirty patients were recruited for each group (CI: 95%). Patients were divided into two groups: Patients who had intraoperative SHP block (Hypo; n=30), and patients who did not have intraoperative SHP block (No-Hypo; n=30). Patients who were under the age of 18, underwent epidural catheterization and / or additional pain management modalities (transversus abdominis plane blocks, local wound site infiltration, quadratus lumborum block... etc.), operated for malignancy, operated by using a different surgical approach (i.e. vaginal hysterectomy), and prescribed preoperative antidepressants or gabapentinoids were excluded from the study.

Duration of operation was calculated in minutes from incision to skin to skin closure. Postoperative pain assessed by 10 cm Visual Analogue Scale (VAS). Pain scores were assessed in post-anesthesia care unit (PACU), and at ward (at 1st, 6th, 12th, 24th and 48th hours). Rescue analgesic time was calculated in minutes as the time interval between the last administration of analgesic intraoperatively and the first analgesic demand in surgical ward. Postoperative nausea and vomiting, hospital stay time, total analgesic requirements of patients in PACU and in surgical ward were recorded.

Statistical Analysis: Study data were analyzed by using IBM SPSS Statistics Version 24. Mann Whitney-U test was used for numerical values which do not meet normal distribution, independent sample t test was used for body mass index, Chi-square test was used to analyze the discrete variables, and p value <0.05 was considered statistically significant. Friedman's test /post-hoc test was used to analyze the repeated measures, and Wilcoxon signed-rank test was used for paired comparison of the repeated measures. Bonferroni corrected significance was considered as p<0,0033.

Ethical Consideration: This study was approved by the Kocaeli University's Institutional Review Board (IRB KÜGOKAEK #2017/285/14.22) and written informed consent was obtained from all subjects participating in the trial. All procedures followed were in accordance with the ethical standards of the responsible committee on human experimentation and with the Helsinki Declaration of the World Medical Association.

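### Groups defined by receipt of the block are compared only with unadjusted tests, while the objective is worded as the block's effect, so a prognostic imbalance could be read as a block effect.

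*Combined protocol and SAP*

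**What the plan says.** The Objectives paragraph sets out to "evaluate the effect of intraoperative superior hypogastric blocks on postoperative pain management". Design and Subjects describes a non-randomised study: "Sixty female patients who underwent elective abdominal hysterectomy were included in the prospective observational cohort study". Methods forms the groups by what patients received: "Patients were divided into two groups: Patients who had intraoperative SHP block" (n=30), against those who did not have it (n=30). No randomisation, matching, stratification or rule for receiving the block is described.

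Confounding is limited only by restriction. Patients with an epidural catheter or another analgesic technique are left out, and so are those "operated for malignancy, operated by using a different surgical approach (i.e. vaginal hysterectomy), and prescribed preoperative antidepressants or gabapentinoids were excluded from the study".

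Statistical Analysis names the Mann-Whitney U test for non-normal numerical values, an independent-sample t test for body mass index (BMI), chi-square for discrete variables, and Friedman and Wilcoxon signed-rank tests for repeated measures. It names no regression, propensity, matched or stratified analysis. BMI is compared between the groups but is not used as a covariate.

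**The concern.** An unadjusted comparison estimates a block effect only if the groups are alike, apart from chance, in everything else that predicts the outcome. Randomisation would secure that, but this design does not have it. Whatever decided who got the block (a surgeon's habit, a calendar period, patient characteristics) may also be related to pain. The exclusions do not balance adult age, BMI, benign indication or the reason for receipt.

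If such a factor differs between groups, the listed tests cannot separate it from the block, and p<0.05 no longer carries a 5% error rate for the claim in the objective. A reader of the results could not tell a block effect from a selection effect.

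**Working it through.** **Do the repeated-measures tests help?** Pain is recorded at six times, PACU plus five on the ward: "Pain scores were assessed in post-anesthesia care unit (PACU), and at ward (at 1st, 6th, 12th, 24th and 48th hours". All pairs of six times number 6×5/2 = 15, and 0.05/15 = 0.0033, which reproduces the stated Bonferroni level. That fits comparisons between times within patients, which do not address confounding between groups.

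**Inputs.** From the document: 30 per group and a 0.05 level (taken as two-sided). The document gives no baseline values, SDs or correlations, so the following are assumptions: no true block effect; one factor with within-group correlation r with pain of 0.2, 0.3 or 0.5; a group difference D in that factor of 0.25 or 0.5 SD; a VAS SD of 2 cm.

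**Formulas.** Spurious difference = r × D outcome SDs, or r × D × 2 cm. With SE = sqrt(2/30) = 0.258, the approximate false-positive rate is P(Z > 1.96 − rD/SE) + P(Z < −1.96 − rD/SE).

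Example, r = 0.5 and D = 0.5: rD = 0.25; 0.25/0.258 = 0.968; P(Z > 0.992) + P(Z < −2.928) = 0.160 + 0.002 = 0.162.

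Simulated Mann-Whitney rates (normal data, 40,000 replicates) beside the approximation:

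| r | D (SD) | Spurious difference | Normal approximation | Simulated Mann-Whitney |
|---|---|---|---|---|
| 0.2 | 0.25 | 0.10 cm | 5.4% | 5.3% |
| 0.3 | 0.25 | 0.15 cm | 6.0% | 5.9% |
| 0.5 | 0.25 | 0.25 cm | 7.7% | 7.4% |
| 0.2 | 0.5 | 0.20 cm | 6.7% | 6.4% |
| 0.3 | 0.5 | 0.30 cm | 8.9% | 8.6% |
| 0.5 | 0.5 | 0.50 cm | 16.2% | 15.4% |

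**Effect of adjustment.** Linear regression on group plus that factor rejects in 4.8 to 5.2% of replicates with ordinary standard errors and 4.3 to 4.7% with robust (HC3) ones. Adjusting only for an unrelated factor at D = 0.5 leaves 6.7, 8.8 and 15.9% for r = 0.2, 0.3 and 0.5. The gain is therefore confined to factors that are measured.

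**Would a baseline test be enough?** With 30 per group, a t test detects a 0.5 SD imbalance with power 0.478, and 0.25 SD with power 0.159. At D = 0.5, when that test is non-significant, the unadjusted outcome test rejects in 5.2, 5.7 and 6.8% of replicates. The rate when it is significant follows from the overall rate:

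- r = 0.2: (0.064 − 0.522×0.052)/0.478 = 0.08
- r = 0.3: (0.086 − 0.522×0.057)/0.478 = 0.12
- r = 0.5: (0.154 − 0.522×0.068)/0.478 = 0.25

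**Precision cost.** In simulation with a skewed 0–10 score, three covariates, imbalance up to 0.5 SD and r up to 0.5, the CI width relative to unadjusted was 0.91 to 1.06 with ordinary SE and 0.93 to 1.09 with HC3, so about −9% to +9%. A two-level surgeon or period covariate costs more. If it explains no outcome variance, the CI widens by 1/sqrt(1 − φ²), where φ is its correlation with group. For an 80/20 versus 20/80 split, φ = 0.6 and the factor is 1/sqrt(0.64) = 1.25. For 90/10 versus 10/90, φ = 0.8 and it is 1/sqrt(0.36) = 1.67.

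**The case against.** The strongest reply concerns size and reach. The design is openly labelled observational, and the exclusions already remove several obvious confounders. No figure in the document supports any particular correlation or imbalance, and at r = 0.2 to 0.3 the error rate is only 5 to 9%. If a recorded factor shows no significant imbalance, adjusting for it gains little. If the driver is unrecorded, adjustment does not remove its effect. Nothing in the document shows that BMI, age or indication predicts pain or decided receipt. Any covariate set would be chosen after the end of the study, which the document dates as "Study Completion (Actual): July 24th, 2018".

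All of this stands, and it limits both the weight of the point and what can be asked for. It does not remove the point. Restriction leaves open the factors it does not cover. A baseline test misses a 0.5 SD imbalance about half the time and is silent on unrecorded drivers. The gap between an observational comparison and an effect-worded objective is in the text whatever the size of any imbalance.

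A reader might go further and infer that the observed group differences are confounded. The document reports no baseline comparison and no imbalance, and gives no direction for one, so it does not support that. A reader might also infer that adjusted models are needed for every outcome, or that the mean of the six VAS scores should become the main outcome. It is true that no primary outcome is named although "Total sample size was determined by performing a power analysis". That is a separate matter from confounding, and those choices are optional.

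**Conclusion.** The point holds as a mismatch between an effect-worded objective and an uncontrolled comparison. For one factor with an assumed correlation of 0.2 to 0.5 with pain and an assumed imbalance of 0.25 to 0.5 SD, the nominal 5% error rate becomes about 5 to 15%. At an assumed VAS SD of 2 cm, the spurious difference is 0.1 to 0.5 cm. Larger assumed values give larger rates, but the document offers no support for them. The true size is unknown and may be nil. Adjustment restores about 5% only for factors that are recorded and correctly modelled. The point is worth correcting because the wording change and a BMI-adjusted estimate are cheap. It is not a finding that the results are wrong.

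**What to change.** 1. Word the objective and conclusion as an association between block receipt and postoperative pain, and state how receipt was decided as the basis for that wording.
2. Beside the unadjusted tests of the VAS scores, report the group difference with a 95% CI from a linear model with robust or bootstrap CI. Adjust for BMI, which is already collected, and for age and indication where recorded. Label this a post hoc sensitivity analysis. Operation duration is best left out of this set: "Duration of operation was calculated in minutes from incision to skin to skin closure", so an intraoperative block may fall inside the interval.
3. If surgeon or period decided receipt and the groups overlap on it, add it as a covariate. If they do not overlap, state that it cannot be separated from the block.

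The cost is two wording changes, one small model per VAS time reported (six at most), and possibly a chart check of 60 patients for age and indication. The covariates are chosen after completion, so each adjusted result should stand beside its unadjusted one. The CI may change by about −9% to +9% for three modestly imbalanced covariates, but widen by about 25 to 67% if surgeon or period is strongly tied to the block. Unmeasured confounding remains in every case.

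### Does the exclusion of patients with an epidural, plane block or wound infiltration need a time limit to avoid selection after the hypogastric block decision?

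*Combined protocol and SAP*

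**What the plan says.** The Methods list the exclusions in one sentence. The criterion at issue removes patients who "underwent epidural catheterization and / or additional pain management modalities (transversus abdominis plane blocks, local wound site infiltration, quadratus lumborum block... etc".. It gives no time window, and its list is open-ended. Later in the same sentence a drug criterion does carry a time word: "prescribed preoperative antidepressants or gabapentinoids were excluded from the study".

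The Design and Subjects paragraph says that the sixty patients "were included in the prospective observational cohort study". The groups are "Patients who had intraoperative SHP block (Hypo; n=30), and patients who did not have intraoperative SHP block (No-Hypo; n=30"). No allocation method is described, and the documents do not say when or by whom the decision to give the block was made.

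The Methods then describe follow-up: "Pain scores were assessed in post-anesthesia care unit (PACU), and at ward (at 1st, 6th, 12th, 24th and 48th hours".). The "total analgesic requirements of patients in PACU and in surgical ward were recorded". Rescue time is "the time interval between the last administration of analgesic intraoperatively and the first analgesic demand in surgical ward".

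**The concern.** Restricting a cohort on something fixed before exposure is ordinary eligibility. Restricting it on something that happens after exposure is not, because that event may be a consequence of the exposure and may share causes with the outcome. Here an added plane block or wound infiltration could be given at closure, or during the 48 hours of follow-up, because the patient was in pain or was expected to be. If patients without the hypogastric block received such techniques more often, the painful end of that group would be removed and the block's benefit understated. The opposite pattern would overstate it.

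The drug criterion has a time limit and the technique criterion has none, which makes the omission look like a real difference in scope. The open list leaves the excluded set undefined. The tests named under Statistical Analysis compare the retained patients and cannot correct for who was removed. With no exclusion counts, a reader cannot rule the problem out.

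**Working it through.** **1. The criteria side by side.**

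| Criterion in the Methods | Time word? | Plain reading |
|---|---|---|
| Epidural or additional pain technique | none | no other regional technique |
| Operated for malignancy | none | benign indication only |
| Different surgical approach | none | abdominal route only |
| Antidepressants or gabapentinoids | preoperative | describes the prescription |

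Two other criteria also lack a time word and read as plain restrictions on who forms the cohort. The contrast with the drug criterion is therefore weak evidence that late exclusion was intended. All the named examples are regional or local techniques, which fits the aim of making the hypogastric block the only such technique compared. Systemic analgesics taken for pain in PACU or on the ward are recorded outcomes, so the usual response to postoperative pain does not lead to exclusion. The text does not settle the order of events within the operation.

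**2. Size if late exclusion did occur.** The documents give no exclusion counts, so rates and slopes are assumptions. Take pain as standard normal with no true group effect. The probability of exclusion is 1/(1 + exp(−(a + b × pain))), with a set separately in each group to give the assumed rate. The bias is the difference in mean pain between the retained groups.

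| Slope b (odds ratio per SD) | 10% vs 3% | 20% vs 5% | 30% vs 10% |
|---|---|---|---|
| 0 (1.00) | 0 | 0 | 0 |
| 0.25 (1.28) | 0.017 | 0.037 | 0.049 |
| 0.5 (1.65) | 0.034 | 0.072 | 0.094 |
| 1.0 (2.72) | 0.062 | 0.126 | 0.162 |
| 1.5 (4.48) | 0.081 | 0.162 | 0.205 |

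Entries are in SD units. Swapping the rates reverses the sign. Equal rates with equal slopes give zero. If the choice rests on expected pain that correlates 0.5 with later VAS, the bottom row halves to 0.041, 0.081 and 0.103.

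**3. Against sampling error.** With 30 per group the standard error is √(2/30) = 0.258 SD without selection, and falls to about 0.24 SD as selection trims the variance. The largest entry is 0.205/0.235 = 0.87 standard errors. The two-sided 0.05 error rate runs from 0.051 to 0.141 over the non-zero slopes, and is at most 0.08 in 9 of those 12 cells. The 0.141 cell needs about 30/0.70 = 43 candidates in one group and 30/0.90 = 33 in the other to retain 30 each.

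**4. One rule in both groups.** Suppose the same pain-based rule applied to everyone. With no true effect the bias is zero, so there is no excess of false positives. For a true effect, the plan gives no planning difference. As an assumption, take the difference that 30 per group detects with 80% power: √(2/30) × (1.960 + 0.842) = 0.72 SD. With 10% to 30% of No-Hypo excluded and slopes of 0.5 to 1.5, the observed difference is 0.71 down to 0.58 SD, always toward no difference. A sharp threshold that excludes 5%, 10% or 20% of No-Hypo gives 0.64, 0.58 or 0.50 SD.

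**5. An extreme case.** If every patient above a pain threshold were removed from No-Hypo and none from Hypo, with no true effect, the No-Hypo mean would fall by 0.11, 0.20 or 0.35 SD at 5%, 10% or 20% removed. The last exceeds one standard error (0.35/0.258 = 1.4). It requires a perfect threshold in one group and no exclusion in the other, which nothing in the documents suggests.

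**The case for a change.** The strongest case for a change is that the wording does permit exclusion after the block decision and nothing elsewhere narrows it. Unequal handling of the groups is not needed for harm: if the block works, one common rule already shrinks the observed difference. One clause would resolve the doubt, and the investigators could close the list and keep patients with later techniques in their group.

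The textual point stands, and so does the possible attenuation. The proposed repair has three difficulties.

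- A cut-off at the decision to give or withhold the block needs a time that the documents never define and that patients without the block may not have.
- Keeping patients with a later technique, and using their VAS scores as observed, estimates the effect of the block together with whatever care followed. The stated objective is the effect of the block itself. Each target is defensible, so this is a choice of question and not the correction of an error.
- Counting any technique given after surgery as a rescue event would alter rescue time, which ends at the first demand on the ward. A technique given in PACU falls between the two definitions.

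The study was completed in July 2018, so data on excluded patients may not exist to re-analyse.

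**Conclusion.** No change to the plan follows. The missing time point and the open list are details that an analyst would settle sensibly by reading the criterion as no other regional technique. The report can state when the criterion was applied, name the techniques, and give exclusions by group, reason and timing. If any occurred after surgery and data exist, a sensitivity analysis that includes them is natural; otherwise the possible selection is a limitation to mention.

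The bias is possible but not demonstrated. Under the graded scenarios it is at most about 0.21 SD, less than one standard error, and its direction is unknown. It exceeds one standard error only under the extreme one-sided threshold with 20% removed. All of this rests on assumed exclusion rates and an assumed dependence on pain. The conclusion would need revisiting if the records showed frequent exclusions after surgery that differed between groups. Non-random allocation remains the larger threat to this comparison.

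### Pain is scored only after surgery and the non-randomised groups are compared without adjustment, so any preoperative pain difference is mixed into the estimated block effect

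*Combined protocol and SAP*

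**What the plan says.** The combined protocol and SAP sets out to evaluate the effect of the intraoperative block on postoperative pain management (Objectives).

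- **Design and Subjects:** "Sixty female patients who underwent elective abdominal hysterectomy were included in the prospective observational cohort study". The groups are defined by what was received: "Patients who had intraoperative SHP block (Hypo; n=30), and patients who did not have intraoperative SHP block (No-Hypo; n=30". No randomisation, matching or assignment rule is described.
- **Methods, pain assessment:** "Postoperative pain assessed by 10 cm Visual Analogue Scale (VAS", and "Pain scores were assessed in post-anesthesia care unit (PACU), and at ward (at 1st, 6th, 12th, 24th and 48th hours". That is six times, all after surgery. No preoperative score or pain history appears anywhere.
- **Statistical Analysis:** "Mann Whitney-U test was used for numerical values which do not meet normal distribution", with a t test for body mass index and chi-square for discrete variables, and "p value <0.05 was considered statistically significant". Friedman and Wilcoxon signed-rank tests cover the repeated scores, and "Bonferroni corrected significance was considered as p<0,0033". No regression, ANCOVA, matching or propensity method is named.

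**The concern.** The objective is worded as an effect, but the groups were not formed by chance. If patients with more, or less, existing pain were more often given the block, and if existing pain carries over into postoperative scores, then part of the VAS difference between Hypo and No-Hypo would be there without any block effect. The bias could run in either direction.

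Nothing in the analysis plan can remove it. The Mann-Whitney test takes no covariates, and the Friedman and Wilcoxon tests compare times within patients, so they do not correct a group imbalance. Body mass index and operation time are recorded, but neither is entered as a covariate and neither stands in for baseline pain.

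There is a second, smaller loss. Even with balanced groups, a baseline score correlated with the outcome would sharpen the comparison at the fixed size of 30 per group.

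**Working it through.** **1. Is the baseline score really absent, or just left out of the list?** The corrected threshold shows how many times entered the repeated-measures analysis. Bonferroni over all pairs of k times is 0.05 / [k(k − 1)/2]:

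- k = 5: 0.05/10 = 0.0050
- k = 6: 0.05/15 = 0.0033, the stated figure
- k = 7: 0.05/21 = 0.0024

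Six times match PACU plus the five ward times. A seventh, preoperative score does not fit.

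**2. Inputs.** From the documents: 30 per group and alpha 0.05 (sidedness not stated; two-sided assumed). Not in the documents, so assumed: the within-group correlation r between preoperative and postoperative VAS, taken as 0.3 to 0.5, and the baseline imbalance g between groups, taken as 0.25 or 0.5 SD. Results are in SD units because no VAS standard deviation is given.

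**3. Bias in the unadjusted difference.** Bias = r × g.

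- g = 0.25: 0.3 × 0.25 = 0.075 SD, up to 0.5 × 0.25 = 0.125 SD
- g = 0.5: 0.3 × 0.5 = 0.15 SD, up to 0.5 × 0.5 = 0.25 SD

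**4. False-positive rate with no true block effect.** Simulated Mann-Whitney and ANCOVA tests, normal data, 30 per group, 20,000 runs per row:

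| g (SD) | r | Mann-Whitney | ANCOVA on baseline |
|---|---|---|---|
| 0.25 | 0.3 | 5.6% | 5.0% |
| 0.25 | 0.4 | 6.2% | 4.9% |
| 0.25 | 0.5 | 7.3% | 4.9% |
| 0.5 | 0.3 | 8.2% | 4.6% |
| 0.5 | 0.4 | 11.1% | 5.2% |
| 0.5 | 0.5 | 15.5% | 5.0% |

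A normal approximation agrees. The standard error is sqrt(2/30) = 0.258 SD, so a bias of 0.15 SD is 0.15/0.258 = 0.58 standard errors, giving about 9%. A bias of 0.25 SD is 0.97 standard errors, giving about 16%. At g = 0.25 it gives 6 to 8%.

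**5. What adjustment does not remove.** With a further unmeasured bias of 0.25 SD from another source, ANCOVA on baseline pain still rejects in roughly 15 to 19% of runs across these settings.

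**6. Precision.** The plan gives no target difference, SD or power, so its sample size cannot be reproduced. With 30 per group, a two-sided t test has 80% power for 0.736 SD. Adjustment multiplies this by sqrt(1 − r²) when the groups are balanced:

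- r = 0.3: 0.736 × 0.954 = 0.70 SD
- r = 0.4: 0.736 × 0.917 = 0.67 SD
- r = 0.5: 0.736 × 0.866 = 0.64 SD

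The residual variance falls by r², that is 9 to 25%. For scale, the step 3 bias at g = 0.5 is 0.15/0.736 = 20% to 0.25/0.736 = 34% of the detectable difference.

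**The case against.** A reader might infer that preoperative pain is a likely confounder here. The documents do not support that. Confounding needs a link to block use as well as to the outcome, and nothing is said about who decided on the block, when or why. Assignment by operator or by theatre list would fit the text equally well. The link to postoperative pain is also assumed. The exclusions (malignancy, antidepressants, gabapentinoids, other blocks) may narrow the spread of baseline pain, though they neither measure nor balance it.

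The figures depend on the chosen imbalance. At 0.25 SD the inflation is slight. The precision gain at r = 0.3 is small, and smaller still if the groups are imbalanced: with a 0.5 SD imbalance the detectable difference is about 0.72 SD instead of 0.70. The simulation also uses normal data, whereas the plan reserves the Mann-Whitney test for non-normal values.

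A reader might also infer that a baseline score would have made the comparison sound. It would not, because it removes one component of bias, and the wider weakness is an unadjusted analysis of non-randomised groups. Finally, the document gives completion in July 2018, so the score cannot be collected now.

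All of this stands, and it limits the strength and size of the point. It does not remove it: the objective concerns an effect, and the plan has neither the measurement nor the model to separate that effect from baseline pain. Completion limits the remedy but does not make the design choice sound.

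**Conclusion.** The point holds as a limitation of design and analysis. VAS is recorded only after surgery, the groups are not randomised and the tests are unadjusted, so a preoperative pain difference of any size passes into the estimated block effect in proportion to r. Whether such a difference existed, and in which direction, cannot be told from the documents. They do not show that the result is biased or invalid.

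The numerical consequence ranges from negligible inflation to a roughly threefold false-positive rate, depending wholly on assumed values of r and g. The return to 5% with adjustment requires that baseline pain be the only confounder. Possible confounding is the main reason to act. The precision gain is secondary and modest unless r is near 0.5.

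**What to change.** **Design.** Include one preoperative 10 cm VAS. Enter it as a covariate in the between-group VAS analysis, by ANCOVA at each time point or as the baseline term of a repeated-measures model, with a rank-based or robust version if residuals are clearly non-normal. Report the adjusted group difference with its 95% confidence interval. Recording the score without changing the analysis would achieve nothing. The cost is one more VAS mark and one data field per patient and one model degree of freedom, with no extra patients, staff or procedures.

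**Now.** Since the study is complete, check whether the charts hold a preoperative pain proxy, such as the indication for surgery. The documents do not say that this was recorded for analysis, although malignancy had to be identified in order to exclude it. If a proxy is available, adjust for it and report the adjusted difference beside the unadjusted one. If not, state that baseline pain was not measured, state how patients came to receive the block, and describe the result as an association and not as an effect of the block. The cost is chart review and re-analysis, or a change of wording only.

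### Rescue analgesic time has no value for a patient who makes no ward demand and has no end of observation; any such patients would be omitted from the group comparison, biasing it towards no effect

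*Combined protocol and SAP*

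**What the plan says.** The outcome is defined in the Methods (unnumbered paragraph on outcomes). The start of the interval is given first: "Rescue analgesic time was calculated in minutes as the time interval between the last administration of analgesic intraoperatively". Its end is then set at "the first analgesic demand in surgical ward", and that demand is the only event that closes the interval.

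Two nearby items could have supplied a limit, but neither is tied to this outcome. Pain scores are scheduled "at ward (at 1st, 6th, 12th, 24th and 48th hours", so 48 h is the last VAS time. The same paragraph also notes that "hospital stay time, total analgesic requirements of patients in PACU and in surgical ward were recorded", without naming discharge as the end of observation for rescue time.

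The Statistical Analysis section does not name a test for rescue time. By elimination it is the one in "Mann Whitney-U test was used for numerical values which do not meet normal distribution", because the t test is named for body mass index, Chi-square is for discrete variables, and Friedman and Wilcoxon are for repeated measures. No time-to-event method appears.

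**The concern.** A patient who goes through the ward stay without asking for analgesic has a start time and no end time. Her rescue time is undefined, and a rank test run on the available values leaves her out unless a rule says otherwise.

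Whether a patient demands analgesic is itself a possible effect of the block. Restricting the test to those who did so selects on a post-treatment outcome. If the block works, more patients are lost from Hypo than from No-Hypo, and they are the ones with the longest times. The remaining comparison understates the delay and loses power, most of all when the block removes the need for ward analgesic altogether. The study's stated objective is the block's effect on postoperative pain management, so this outcome bears directly on it.

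**Working it through.** **Inputs from the documents.** "Thirty patients were recruited for each group (CI: 95"%), so 30 against 30. The significance rule is "p value <0.05 was considered statistically significant", taken here as two-sided because sidedness is not stated. The last scheduled assessment is at 48 h.

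**The plan's own figure.** The Methods say "Total sample size was determined by performing a power analysis", with no endpoint, effect size, SD or power, so 30 per group can be neither reproduced nor refuted. For orientation, n = 2(z₀.₉₇₅ + z_power)²/d². At 80% power, 2(1.960 + 0.842)²/0.724² ≈ 30. At 90% power, 2(1.960 + 1.282)²/0.837² ≈ 30. So 30 per group corresponds to a standardised difference of about 0.72 or 0.84.

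**Assumed model.** Time to first demand is log-normal with SD 1 on the log scale and a true median ratio of 2. The limit L is 48 h. The medians are assumptions and were varied. The standardised difference on the log scale is ln 2 / 1 = 0.69, just under 0.72, so power a little above 70% with complete data is what one would expect.

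**Share with no demand by L**, for median m: 1 − Φ(ln(L/m)).
- m = 2 h: 1 − Φ(ln 24) = 1 − Φ(3.18) = 0.1%
- m = 4 h: 1 − Φ(ln 12) = 1 − Φ(2.48) = 0.6%
- m = 6 h: 1 − Φ(ln 8) = 1 − Φ(2.08) = 1.9%
- m = 8 h: 1 − Φ(ln 6) = 1 − Φ(1.79) = 3.7%
- m = 12 h: 1 − Φ(ln 4) = 1 − Φ(1.39) = 8.3%
- m = 24 h: 1 − Φ(ln 2) = 1 − Φ(0.69) = 24.4%

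**Power by simulation** (4,000 replicates per row; repeat runs differ by up to about 2 points).

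| Medians, No-Hypo and Hypo | No demand by 48 h | Mann-Whitney, non-demanders omitted | Mann-Whitney, tied at the limit | Log-rank |
|---|---|---|---|---|
| 2 h and 4 h | 0.1% and 0.6% | 71% | 71% | 68% |
| 4 h and 8 h | 0.6% and 3.7% | 67% | 72% | 68% |
| 6 h and 12 h | 1.9% and 8.3% | 64% | 73% | 68% |
| 12 h and 24 h | 8.3% and 24.4% | 46% | 73% | 69% |

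In the last row the expected numbers omitted are 30 × 0.083 ≈ 2.5 and 30 × 0.244 ≈ 7.3.

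**Effect on the estimate, last row.** The median among demanders is m·exp(Φ⁻¹(½Φ(ln(L/m)))). For No-Hypo, 12·exp(Φ⁻¹(0.459)) = 12·exp(−0.104) = 10.8 h. For Hypo, 24·exp(Φ⁻¹(0.378)) = 24·exp(−0.311) = 17.6 h. The apparent ratio is 17.6/10.8 = 1.63 against a true 2.

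**A different mechanism.** Suppose the block leaves demand times unchanged among demanders (exponential, median 120 min in both groups) but a share of Hypo never demands, and everyone in No-Hypo does. With shares of 10%, 20% and 30%, power is about 5%, 4% and 4% with omission, against 9%, 27% and 53% with all patients kept. Omission then leaves no more than the nominal 5% error rate, so the test is blind to the effect.

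**The case against.** A reader might infer that the patients helped most by the block were in fact dropped. The documents do not support that: they do not say that any patient made no ward demand, or that any was excluded. The setting makes few non-demanders plausible. The protocol describes significant pain after this operation and excludes patients with epidurals, other blocks or wound infiltration, so nearly everyone may have asked for analgesic within 48 h. In that case the gap has no numerical effect, as the first row of the table shows. This objection stands, and it is why the point is conditional.

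A reader might also take the 46% row as the expected loss. It rests on assumed medians of 12 h and 24 h, and the documents give no demand times with which to choose between the rows.

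Two further points limit the consequence. Rescue time is not designated the primary outcome, and total analgesic requirement is also recorded, where a patient with no ward demand can count as zero. The bias from this rule is towards no effect, so it would not by itself create a false benefit. Neither point repairs the definition: an outcome that is reported should have a value, or a stated censoring rule, for every patient.

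**Conclusion.** The gap in the definition is real and should be closed; how much it matters cannot be determined from the documents. What is established is that the outcome exists only for patients with a ward demand, that no limit or censoring rule is given, and that none of the named tests handles censoring. What follows conditionally is omission of any non-demanders and a bias towards no effect, provided the block lengthens or removes demand.

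Under the log-normal assumptions the loss of power runs from about nil to 27 points (73 − 46). It is larger, 49 points (53 − 4), if the block acts only by removing demand in 30% of Hypo. The number with no demand in each group is the one fact that would settle which case applies.

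**What to change.** - Set the end of observation for rescue analgesic time at 48 h, or discharge if earlier, counted from the same start as the outcome.
- Keep all 60 patients. In the Mann-Whitney test, rank those with no demand as tied at the longest time. Patients discharged early without a demand are ranked with them; state this as an assumption.
- As a supporting analysis, give Kaplan-Meier curves and a log-rank test, censoring at the limit or at discharge.
- Report the number per group with no ward demand. This is the essential item even if nothing else changes.
- Label the change as post hoc, because the document gives an actual completion date of July 2018.

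**Cost.** No new patients are needed, but observation end times must be recoverable from the hospital stay and analgesic records, which the documents do not confirm. A post hoc change to a completed study carries less weight than a pre-specified rule. Log-rank should support the rank test, not replace it: used alone it costs a few points when almost everyone demands analgesic (68% against 71% at medians of 2 h and 4 h). Mann-Whitney with ties at the limit avoids that loss and is the smaller change.
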